This community-partnered study seeks to explore, describe, and measure the implementation and impact of an innovative pilot intervention, the Whole Person Care (WPC) Program, a network coach intervention that addresses two key challenges for recently incarcerated youth: poor care coordination in the “behavioral health cascade” and need for more positive support from the social network. Los Angeles (LA) County has the largest justice system in the US and has begun implementing the WPC network coach intervention to enhance linkages to community behavioral health services. WPC is based on the successful Transitions Clinic model, an intervention with demonstrated efficacy in linking recently incarcerated adults to needed healthcare and improving health outcomes. The model has yet to be implemented for reentry youth, but has the potential to be transformative at the critical developmental stage of adolescence, when peer social networks are highly dynamic and youth behaviors can affect lifelong trajectories. WPC network coaches will receive formalized training modeled after the adult Transitions Clinic approach and will serve as a formerly incarcerated adult role model who provides care coordination and social support to facilitate access to needed behavioral health services. Tailored for reentry youth, WPC will also include a social network component whereby coaches are trained to actively guide youth toward pro-social peers and adults. The Principal Investigator, [name], has been working closely with LA County and this study capitalizes on a unique opportunity to study the WPC program. We propose an exploratory and observational study of WPC, using a community-partnered, participatory research (CPPR) approach. While we anticipate that this data collection and analysis will have sufficient power to detect differences between groups, the relative paucity of information known about this topic and this study population ensure that the data collected will be novel and provide an opportunity to inform intervention design and refinement.

Specific aims are to:

- 1) Describe the social networks of transition-age youth (TAY) exiting jail or juvenile detention.

Hypothesis 1: Participants will describe their social networks. We expect that social networks will include individuals who have a history of substance use, as well as individuals who do not have a history of substance use and/or discourage the use of substances.

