- 2) Measure the impact of the Whole Person Care (WPC) intervention for TAY exiting jail in decreasing rates of 30-day use and risky use of marijuana and alcohol.

Hypothesis 2: Incarcerated youth enrolled in the WPC intervention will have less substance use 3 and 9 months post-release compared to their peers who are not receiving the WPC intervention.

- 3) Test whether the WPC intervention decreases recidivism and increases receipt of behavioral health services (secondary outcomes).

Hypothesis 3: Youth participating in WPC will have less recidivism and higher rates of receipt of behavioral health services.

4): Examine whether recently incarcerated youth receiving the WPC intervention report healthier social networks (lower proportion of peers engaging in risky behaviors and a higher number of supportive adults) than control youth.

Hypothesis 4: Youth receiving the WPC intervention will have a lower proportion of peers engaging in substance use and a higher number of supportive adults in their social networks compared to their peers in the control group.

5) Identify effective approaches for achieving linkages to care during reentry for TAY who have high community health service utilization versus low community health service utilization.

Hypothesis 5: TAY will describe the interrelationship between social networks, substance use, and care utilization, providing insight that can guide the development and implementation of a social network intervention to reduce TAY substance use during reentry.

IV. Research Design and Methods

We will use a community-partnered participatory research (CPPR) approach, collaborating closely with the LA County Health Agency and the Probation Department to develop and measure the impact of a network coach intervention to reduce adolescent substance use and other markers of healthy reintegration among recently incarcerated adolescents. We will conduct an observational study to help us gain insight of the intervention, including the implementation and study population. Note: There are two populations in this study: (1) Transition age youth (TAY), ages 18-24, exiting the adult criminal system and (2) TAY, ages 16-19, exiting the juvenile justice system. Study methods for each population are described below, starting with the adult population.

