****TAY Exiting the Adult Criminal System (ADULT POPULATION)****

Study population:

Participants who are eligible for the Whole Person Care—Los Angeles (WPC-LA) Reentry post-release program will be eligible for the adult population of this study. The WPC Reentry program, implemented by the Los Angeles County Health Services Department, links jail inmates with community-based health, behavioral health, and social service providers as they return to the community. The intervention connects participants to Community Health Workers (CHWs) with a prior personal history of incarceration. CHWs assist participants in engaging with community-based health, behavioral health, and social service providers during reentry to the community. Services provided include mentorship and social support; health and social service navigation; linkage to housing, employment, education, legal assistance and social supports; accompaniment to key health and behavioral health appointments; assistance with adherence to appointments, treatments and medications; and connection to transportation. The mentorship and social support aspects of the intervention will indirectly target the social networks of participants. The WPC intervention is an existing intervention. The WPC intervention enrolls 750 individuals per month across LA County; approximately 12% are transition age youth ages 18-24. Participants are invited to this program while detained by the WPC case manager. Thus, WPC is a voluntary program. The WPC case manager is responsible for determining eligibility for the WPC reentry program and enrollment in the WPC program, not the research staff.

Recruitment and Consent:

We will recruit 160 adults exiting the LA county justice system – 80 who have enrolled in the WPC program and 80 have not. We anticipate enrolling participants over an approximate 9 month window, aiming to recruit about 9 individuals per arm (WPC and non-WPC) each month. This represents approximately 10% of the eligible population each month for each arm.

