The research team will also invite a sub-set of survey participants from the Centinela Valley (eligible zip codes included as an attachment) to participate in focus groups outside of detention. Participants will be asked to participate in one focus group, lasting up to one-hour. Based on survey results, focus groups will be purposefully designed to include groups with individuals who are high versus low care utilizers. Utilization rates will be determined based on both youth survey responses and medical record abstraction. These rates will then be reviewed by the study data analyst and investigators to determine the appropriate cut point for the dichotomization of health services utilization. Two focus groups will be conducted with TAY who exited the county jail and two other focus groups will be conducted with youth who were released from the juvenile justice system.

Time required of subjects:

Total time: up to 3 hours

Recruitment and consent: 10 minutes

Baseline survey: 30 minutes

3-month follow-up survey: 30 minutes

6-month follow-up survey: 30 minutes

Focus group interview: 60 minutes (optional)

Fidelity of the Intervention:

We will utilize 2 methods for assessing fidelity of the intervention: 1) Youth surveys: the follow-up youth surveys for those in the intervention group will include a WPC fidelity form to assess whether core components of the intervention occurred, including measuring the frequency and duration of interactions with coaches, youths' perceptions of coaches and the usefulness of the WPC program. 2) Coach surveys and interviews: Network coaches will complete a WPC fidelity form (survey) and we will conduct qualitative interviews with network coaches to assess their perceptions of successes and challenges with adherence to the WPC protocol. Only interviews with coaches will be audio recorded. Coaches will have the opportunity to listen, edit, and delete the recordings. These assessments will provide information for refinement of the intervention and pilot data to inform the R01 submission.

Statistics and Data Analysis

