#### **Aim 3: Examine whether recently incarcerated receiving the WPC intervention report healthier social networks (lower proportion of peers engaging in risky behaviors and a higher number of supportive adults) than control young people.**

*Hypothesis 3:* Young people receiving the WPC intervention will have a lower proportion of peers engaging in substance use and a higher number of supportive adults in their social networks, compared to young people in the control group.

Regardless of whether WPC lowers drug use, recidivism, or use of support services, the social network analysis of reentry young people will give valuable information on changes in social networks among recently incarcerated young people during reentry. In addition, WPC is designed to encourage prosocial peer network formation, and the social network analysis will help determine why the intervention did or did not demonstrate the expected effect. Understanding strategic levers for how young peoples' social networks can be altered is critical to developing sustaining solutions to young people substance use and incarceration. We will measure how social networks function for young people and whether the insertion of a supportive adult can create linkages to substance use services and promote healthier social networks. We will use the approach described in Baron and Kenny (1986) to evaluate whether our data are consistent with a model in which social networks mediate the relationship between WPC receipt and substance use. Additionally, if analyses for Aims 1 and Aim 2 do not indicate improvement overall in the intervention group, we will conduct exploratory analyses to identify subgroups of young people whose Aim 1 and Aim 2 outcomes improve and examine their social networks.

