Primary social network measures will include the change in proportion of peers using substances (alcohol, marijuana, other drugs), limited to those whom the subject interacts with within the last month. We will compare baseline social network characteristics of the intervention and control groups and control for these measures if significant differences are noted. To test whether young people receiving WPC report a lower proportion of peers in their network engaging in substance use, we will conduct a mixed effects binomial logistic regression model accounting for repeated measurements within students. We will control for baseline demographic characteristics, as well as any variables found to be differential between the intervention and control groups. We will also examine the number of non-using supportive adults in their network using a mixed effects binomial logistic regression model. Finally, based on young peoples' descriptions of the connections between alter-alter pairs, we will construct a measure of peer network density (number of alter-alter connections out of total possible) for the peer substance-using and non-using networks. We will use mixed effects models to investigate whether network structure differs between study arms and whether intervention young people report stronger connections to healthy peers and adults.

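### The SAP predicts a higher number of supportive adults but analyses non-using supportive adults with a binomial model that has no stated denominator, and it does not say whether the WPC worker is counted

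*SAP*

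**What the plan says.** **Hypothesis.** SAP Aim 3, Hypothesis 3, has two halves. Youth receiving WPC "will have a lower proportion of peers engaging in substance use", and they will have "a higher number of supportive adults in their social networks". The Protocol (Hypothesis and Specific Aims, Hypothesis 4) words the adult half the same way: "a higher number of supportive adults in their social networks compared to their peers in the control group". Neither hypothesis requires that the adults be non-users.

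**Analysis.** SAP Aim 3 assigns a mixed effects binomial logistic model to the peer proportion. It then gives the adults the same kind of model: "We will also examine the number of non-using supportive adults in their network using a mixed effects binomial logistic regression model". The Protocol (Statistics and Data Analysis) does likewise. Neither document states a number of trials for the adult outcome, a fixed length for the alter list, or a cut-point. The only limit on alters is how recently or how often the youth has contact with them, and it is attached to the peer measure.

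**The worker.** The Protocol (Hypothesis and Specific Aims) says the coach "will serve as a formerly incarcerated adult role model who provides care coordination and social support". SAP Aim 3 sets out to measure "whether the insertion of a supportive adult can create linkages to substance use services". Neither document says whether that adult enters the count.

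**The concern.** A binomial model suits the peer half of the hypothesis, because a proportion of peers has a natural denominator. The adult half is stated as a number. Three things then stand between the hypothesis and the planned result.

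1. The outcome changes. A supportive adult who uses substances counts under the hypothesis and not under the analysis.
2. The model may estimate something other than a number. If youth name as many people as they wish, a binomial model with alters as trials estimates a share. If the outcome is dichotomised, it estimates the odds of having at least one such adult.
3. The intervention provides one supportive adult by design. If youth name that person, the count rises in the intervention arm with no other change in the network.

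At stake is how this half of the hypothesis can be read. Without the denominator, a result could not be read as more or fewer adults. Without a rule for the worker, a positive result could not be read as change in the rest of the network. The main outcome, marijuana use, is not affected.

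**Working it through.** **Plan's own figure.** There is none for this outcome. The SAP's only sample-size figure (17%, about 5 of 30 days) concerns marijuana use and does not bear on this point.

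**Step 1: the outcome.** Hypothesis: supportive adults. Analysis: non-using supportive adults. The two differ whatever the survey looks like.

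**Step 2: what the model estimates.** Let a be the mean number of non-using supportive adults and o the mean number of other alters in the denominator. Subscript 1 is WPC and 0 is control. On an open list the pooled odds ratio is

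OR = (a1/o1) / (a0/o0) = (a1/a0) / (o1/o0),

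that is, the rate ratio for the adults divided by the rate ratio for the other alters. The documents give no network sizes, so those below are assumed.

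| Adults | Other alters | Rate ratio, adults | Pooled OR |
|---|---|---|---|
| 2 to 3 | unchanged | 1.50 | 1.50/1.00 = 1.50 |
| 2 to 3 | up 25% | 1.50 | 1.50/1.25 = 1.20 |
| 2 to 3 | up 50% | 1.50 | 1.50/1.50 = 1.00 |
| 2 to 3 | doubled | 1.50 | 1.50/2.00 = 0.75 |
| unchanged | 8 to 7 | 1.00 | 1/(7/8) = 1.14 |
| unchanged | 8 to 6 | 1.00 | 1/(6/8) = 1.33 |

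The last two rows need all alters as the denominator. They could arise from the first half of Hypothesis 3, if youth drop using peers without replacing them.

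For the planned mixed model the identity is approximate. In large-sample random-intercept fits with independent variation between youth, a pooled 1.50 became about 1.55 when adults rose proportionally. It became about 1.61 when every WPC youth gained one adult.

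**Step 3: fixed list.** With 10 alters per youth and adults 2 to 3, OR = (3/7)/(2/8) = 1.71. The share now moves with the number, and the binomial model is adequate.

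**Step 4: any versus none.** If the outcome is dichotomised, a youth who goes from one such adult to three contributes no change. This too is not the number, and Step 2 does not apply to it.

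**Step 5: the worker.** If a proportion q of WPC youth and a proportion c of controls name a worker, on top of a mean of m other adults, the rate ratio from the worker alone is (m + q)/(m + c). With m = 2, q = 0.6 and c = 0, this is 2.6/2 = 1.30. With c = 0.2 it is 2.6/2.2 = 1.18. With equal naming it is 1.00. Controls could name a worker, since the SAP (Analytic Strategy) says they received pre-release WPC services.

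**Step 6: illustrative rejection rates.** These are simulated stand-in tests, not the planned fits: two-sided 5% level, two follow-ups and 72 per arm (80 × 0.90, applying the SAP's 3-month attrition to both follow-ups, which is an assumption). Counts are Poisson, with gamma variation between youth in the number of adults (coefficient of variation 0.5). Ranges cover no, shared and independent between-youth variation in the other alters.

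| Assumed truth | Count model | Binomial |
|---|---|---|
| Adults 2 to 3, others in step | 94–96% | 5–6% |
| Adults 2 to 3, others unchanged | 95–96% | 71–99.7% |
| Adults unchanged, others 8 to 6 | 5–6% | 48–85% |

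With the worker as the only change (mean of 2 other adults, no controls naming one), the count model rejects in 14, 38, 69 and 90% of trials when 20, 40, 60 and 80% of WPC youth name one. At 60% naming it rejects in 97% with a mean of 1 other adult and in 30% with a mean of 4. Every mean, variance and naming rate here is assumed.

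**The case against.** **The survey may settle the denominator.** This stands. The survey instrument is not among the documents. A reader might infer that the list is open and the model therefore wrong; the documents do not show that. They show that the denominator is not stated.

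**A share has merits.** This stands in part. On an open list a raw count also moves with how many names a youth gives, so the in-step scenario could be a difference in naming, which a share resists. But the hypothesis is about a number, and the total number of alters can be reported beside the count.

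**The figures are built on assumptions.** True, and they are offered only as illustrations. A reader might also infer that the binomial model generally loses power. The table does not support that: with the other alters unchanged, the binomial test can do better or worse than the count, depending on network variation that nobody yet knows.

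**The worker belongs in the count.** This is a legitimate reading. Hypothesis 3 does not exclude the worker, and the SAP treats an inserted adult as part of the mechanism. What remains is that the worker alone does not show change in the rest of the network. The fidelity form does not close the gap: "the follow-up youth surveys for those in the intervention group will include a WPC fidelity form", so it does not cover controls, and nothing links it to the network count.

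**Networks as a target.** The Protocol (Study population) says: "The mentorship and social support aspects of the intervention will indirectly target the social networks of participants". A reader might infer that wider network change is targeted only indirectly. That goes too far. The sentence concerns two aspects of the programme; elsewhere the Protocol says coaches are trained to steer youth actively toward pro-social peers and adults, and SAP Aim 3 says WPC is designed to foster prosocial peer networks.

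**Conclusion.** The point holds as a minor one. The mismatch between supportive adults and non-using supportive adults is certain from the text. The mismatch between a number and a binomial model holds unless the survey fixes the number of alters. Under either a share or an any-versus-none reading, the planned analysis need not test the stated hypothesis. On an open list the pooled odds ratio can be 1.00 when the adults rise by half, and 1.33 when they do not rise at all. These values follow from the assumed networks and are approximate for the mixed model.

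The silence about the worker is also certain from the supplied text. How far it matters depends on how many youth in each arm name one: the effect is nil if naming is equal and large if most WPC youth and no controls do so. Confidence is medium, because the instrument could resolve the denominator and may identify workers.

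**What to change.** 1. Use one outcome, either supportive adults or non-using supportive adults, in both the hypothesis and the analysis.
2. Analyse the number with a mixed-effects Poisson or negative binomial model and report rate ratios. If the survey fixes the number of alters, state that denominator and keep the binomial model. Keep the binomial model for the peer proportion in either case.
3. Where the survey identifies WPC workers, flag them in both arms and report the count with and without them. Base any claim of wider network change on the count without them. If they cannot be identified, say that the worker cannot be separated. Changing to a count model does not remove this problem.
4. Report the total number of alters by arm, because a raw count on an open list also moves with how many names a youth gives.

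The cost is SAP wording and, where alter roles are recorded, one coding flag. There will be two counts to report, and the expected difference is smaller once the worker is excluded. If roles were not recorded, the split is not possible for surveys already done.

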### **Sample Size Estimate**

We estimated power for a 2-arm pilot trial. We plan to recruit and consent 160 transition-age young people exiting jail. With a sample size of 160, we believe that our study will be adequately powered to detect a minimal detectable difference in the percentage of days used marijuana in the past 30 days of 17%, which is equivalent to a decrease of 5 days of marijuana use in a 30-day period. This difference is within the observed effect seen in a prior study of marijuana use among reentry young people, which found a range of intervention effects from 11% to 38%. This calculation assumes 10% attrition rate at 3 months, two-sided test with alpha 0.05, and 80% power.
